Statistical Analysis Plan (SAP)

HIP fracture REhabilitation Programme for older adults (HIP-REP)

ClinicalTrial.gov identifier NCT04207788

Author [name],
MScOT, [name]. student
Department of Sports Science and Clinical
Biomechanics
University of Southern Denmark

SIGNATURE PAGE

Principal
Investigator

—

Picture 21/4 - 2021
[name]

[name] (2021-04-21)

Author

—

[name] 21/4-2021
[name]

[name] (2021-04-21)

Abbreviations

ADL	Activity of daily living
AMPS	Assessment of Motor and Process Skills
MCID	Minimum Clinically Important Difference
QoL	Quality of Life
SAP	Statistical Analysis Plan

Indhold

1. Introduction	4
2. Objectives and hypothesis	4
3. Study design and methods	4
3.1. Sample size calculation	6
4. Outcomes	6
4.1 Primary outcome	7
4.2 Secondary outcomes	7
4.3. Safety outcomes	7
5. Populations and subgroups to be analysed	7
5.1. Populations	7
5.2 Subgroups	7
6. Statistical analysis	8
6.1. Missing data	8
Referencer	9

1. Introduction

The overall aim of this study is to evaluate the efficacy of a Rehabilitation Programme for older adults with hip fracture, focusing on enabling older adults with hip fracture to safely and independently perform Activity of Daily Living (ADL), and thereby enhance their health-related Quality of Life (QoL).

This statistical analysis plan (SAP) gives a more detailed descriptions of the endpoints in the study and the statistical analysis.

2. Objectives and hypothesis

Objective: To evaluate the effect of a HIP-REP on the quality and independence in ADL ability (performance), measured with the Assessment of Motor and Process Skills (AMPS) and health-related QoL measures.

Hypothesis: The HIP-REP will increase the quality and independence in ADL performance, measured with AMPS and health-related QoL measures.

3. Study design and methods

This study is inspired by the Medical Research Councils (MRC) guidelines for Developing and Evaluating Complex Interventions and compromises the third stage of the MRC framework for assessing complex interventions (1). The study is a single-blinded randomized controlled trial, where the effect of HIP-REP, will be evaluated. The study was registered in Clinical trial.gov (<http://clinical trial.gov/>) and approved by the Regional Ethical Committee and Datatilsynet.

Recruitment: The study subjects admitted from the Orthopaedic Ward, Herlev and Gentofte Hospital from 1. February 2020 to 31. December 2020 will be eligible if residence in Herlev, Rudersdal, Furesoe, Lyngby-Taarbaek and Gentofte municipalities (Table 1).

Table 1 Inclusion and exclusion criteria

Inclusion and exclusion criteria – older adults with hip fractures	
Inclusion criteria:	Exclusion criteria
• Aged 65 years or older	• Not expected to be discharged to home or rehabilitation centres in the municipality
• Recent proximal hip fracture (S 72.0 Medial femur fracture, S 72.1, Pertrochantor femur fracture, S 72.2 Subtrochantur femur fracture)	• Not able to speak and/or understand Danish
• Living at home prior to hip fracture in Herlev, Rudersdal, Furesoe, Lyngby-Taarbaek or Gentofte municipalities	• Have prior severe physical and /or mental disabilities
• Ability to give informed consent	

Randomisation: After the initial test (baseline) older adults with hip fracture will equally be divided into the intervention- or control group (1:1) by a computer-generated block randomization in permuted blocks of 4, 6 or 8, and stratified for municipality.

[figure not shown]
Blinding: Those testing the participants at follow-up will be blinded to previous test results and allocation. A person not involved in the rehabilitation or data collection will enter the data, and analysis will be performed blinded for group allocation.

Withdrawal/follow-up: Following the Regional Ethical Committee regulations, older adults with hip fracture or their legal representatives will be informed about the possibility of withdrawing from the study. Withdrawal from the study can occur after informed consent if the older adult regret participation. Reasons for withdrawal or lost to follow-up will be reported in the manuscript and/or flow chart.

Intervention: The main aim of the HIP-REP is to increase the quality of ADL performance and self-rated QoL for the older adults with hip fractures and thereby improve their ability to live independent at the 3-month follow-up. The HIP-REP will be tailored to the need of older adults with hip fracture in a liaison with the health care professionals (HCP).

The study design is visualised in Figure 1 below.

Figure 1 Flowchart of screening and inclusion process

3.1. Sample size calculation

Statistical power calculation is based on the minimum clinically important difference (MCID) for motor skills in AMPS, which is 0.3 logits (2). The power is set to 0.8 and the standard deviation (SD) is 0.50, which gives a sample size of 90 persons (2). Because of expected dropout, 54 elderly with hip fracture are therefore included in each group.

4. Outcomes

This section will present the outcomes investigated to answer the study aims, objectives and hypothesis.

The analyses are described in section 6 Analyses.

4.1 Primary outcome

The primary outcome (AMPS) will be assessed on the third to fifth post-operative day at the hospital (2). AMPS, is a standardized observation-based evaluation tool to measure a persons observed quality of ADL task performance in terms of physical effort and/or fatigue, efficiency, safety and independence (2). Furthermore, the AMPS test will be performed, after completed rehabilitation at 3 months follow-up to identify older adults with hip fractures challenges with Personal Activity of Daily Living (PADL) and Instrumental Activity of Daily Living (IADL).

4.2 Secondary outcomes

Functional Recovery Score (FRS) (3), Health-related QoL: European Quality of Life Scale (EQ-5D) (4) and Verbal Rating Scale (5).

Other data collected: Age, gender, type of fracture, waiting time for surgery, length of stay in acute hospital, marital status, type of dwelling, comorbidity (Charlson Index), 30-days mortality, physical therapy and occupational therapy services, level of education, warranted community-based assistance, inpatient and outpatient treatment since last assessment, usage of home-based services and pain score.

4.3. Safety outcomes

Adverse events: Adverse events are reported at each intervention.

Concomitant interventions: Participation in rehabilitation besides the HIP-REP programme during the study period will be recorded.

5. Populations and subgroups to be analysed

5.1. Populations

Intention to treat (ITT): All randomised participants. This will be the primary population for the analysis.

Per Protocol (PP): All randomised participants completing the whole study period (complete cases). Analysis of the population is seen as a sensitivity analysis to investigate whether conclusions are sensitive to the assumptions that missing data were missing at random.

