5.2 Subgroups

Due to Covid-19 some participants may not have received the entire intervention at home and therefore subgroup analysis restricted to participants received at least three of the planned visits in own home.

6. Statistical analysis

The primary analysis will be a mixed effect model where group (intervention and control) and municipality are fixed, and the patient is random, assuming dropout is at random. The score at the end of rehabilitation after 3 months will be analysed unadjusted and adjusted for baseline score, age, municipality, gender, fracture and type of operation.

The estimated difference in mean change from baseline to 3 months follow-up and the corresponding 95 % confidence interval (CI) will be presented. Stata (StataCorp. 2019) will be used for the statistical analysis.

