6.1. Missing data

When analyses were performed based on the ITT population, multiple imputation (MI) will be performed for both primary and secondary outcomes based on the baseline variables of patient characteristics and the outcome in question.

Referencer

2. Fisher AG, Jones, K B. Assessment of Motor and Process Skills: Skills, Development, standardization and administration: Manual. Fort Collins, CO: Three Star Press; 2010.
3. Fysioterapeuter D. Functional Recovery Score (FRS). 2018.

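### The complete-case analysis cannot test sensitivity to missing at random as Section 5.1 says, and no planned analysis departs from that assumption

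*SAP*

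**What the plan says.** Section 5.1 makes all randomised participants the primary population. It adds a per-protocol set, defined purely by completion of the study and glossed as complete cases, with no adherence criterion. The analysis of that set is called a "sensitivity analysis to investigate whether conclusions are sensitive to the assumptions that missing data were missing at random".

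The analyses it is meant to probe are in Section 6 and Section 6.1. The primary mixed model is fitted "assuming dropout is at random". The 3-month score "will be analysed unadjusted and adjusted for baseline score" and five further covariates. Multiple imputation for the intention-to-treat population is "based on the baseline variables of patient characteristics and the outcome in question".

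The only other restricted analysis is the Covid-19 subgroup in Section 5.2. It concerns home visits received, not missing data. Nothing in Sections 5.1 to 6.1 allows the missing scores to depart from MAR.

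**The concern.** A sensitivity analysis for MAR has to relax MAR, by letting participants with missing outcomes differ from what their observed data predict. The completers analysis does not. It changes how observed predictors of dropout are used, and its own validity condition is generally as strict as MAR or stricter.

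Baseline is measured before allocation (Section 3: "After the initial test (baseline) older adults with hip fracture will equally be divided into the intervention- or control group"), so dropouts have baseline scores. Multiple imputation can use these scores, as can the mixed model if it is fitted to both time points. The completers analysis discards them.

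Two misreadings follow. A gap between the completers and imputed results may be taken as evidence against MAR when MAR holds. Agreement may be taken as support for MAR when it fails and both results carry the same bias. In either case, the effect of outcome-dependent dropout on the AMPS difference goes unexamined while the plan says it is examined.

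**Working it through.** **Inputs from the SAP (Section 3.1).** Difference 0.3 logits, SD 0.50, power 0.8, 90 participants before dropout, 54 per group recruited. Alpha is not stated; two-sided 5% is assumed.

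**The plan's own figure.** Normal approximation: n per arm = 2 × (1.960 + 0.842)² × 0.50² / 0.3² = 43.6, so 44. The t-test version gives 44.6, so 45 per arm and 90 in total, as stated. Recruiting 108 for 90 implies a missing fraction of 1 − 90/108 = 1/6. The SAP does not state this rate.

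**What each analysis assumes.**
- Mixed model and imputation: given the observed data they use, dropouts resemble completers (MAR).
- Adjusted completers: dropout depends on nothing beyond group and the covariates in the model.
- Unadjusted completers: dropout depends on nothing beyond group.

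The first two conditions are not strictly nested if imputation uses extra variables, but none of the three moves towards missing not at random.

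**Illustration.** Assumptions: true difference 0.30, SD 0.50, 1,000,000 per arm, 1/6 missing per arm, and random dropout in control. In the intervention arm the log-odds of dropout fall by 1 per SD of the driving score. Imputation is done within arm from baseline score, adjustment is for baseline score, and r is the correlation between baseline and 3-month score. Estimated differences in 3-month score:

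| Dropout driven by | r | Unadjusted completers | Adjusted completers | Imputation |
|---|---|---|---|---|
| Baseline score (MAR true) | 0.3 | 0.322 | 0.300 | 0.300 |
| | 0.5 | 0.336 | 0.300 | 0.299 |
| | 0.7 | 0.351 | 0.300 | 0.300 |
| 3-month score (MAR false) | 0.3 | 0.372 | 0.366 | 0.366 |
| | 0.5 | 0.374 | 0.356 | 0.357 |
| | 0.7 | 0.373 | 0.338 | 0.339 |

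- Unadjusted gap from imputation: about 0.02/0.04/0.05 when MAR holds, and 0.01/0.02/0.03 when it fails. The gap is larger in the case where nothing is wrong with MAR.
- Adjusted gap when MAR fails: at most 0.001 here and 0.002 in repeat runs, while both estimates are biased by 0.04 to 0.07.
- Slopes 0.5 and 1.5, MAR false: imputation gives 0.338/0.329/0.322 and 0.389/0.374/0.354, so the bias ranges from 0.02 to 0.09.
- Missing fraction 10% or 25% (r = 0.5, slope 1): imputation gives 0.334 or 0.382.
- Same 3-month-score mechanism in both arms: all estimates 0.299 to 0.300, so no bias.

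**At trial size** (54 per arm, 2000 runs, 20 imputations, r = 0.5) the mean absolute gap between adjusted completers and imputation is 0.010 when MAR holds and 0.008 when it fails. The comparison does not separate the two cases.

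**General formula.** With equal missing fractions, bias = fraction × between-arm difference in the dropouts' departure from prediction. In the MAR-false rows that departure is −0.40/−0.34/−0.24 logits in the intervention arm, giving 0.067/0.057/0.040, in line with the table. A departure of 0.25 logits gives 1/6 × 0.25 = 0.042, and 0.5 logits gives 0.083. The residual SD is 0.5 × √(1 − r²) = 0.477/0.433/0.357, so 0.5 logits is 1.05 to 1.4 residual SDs, a large departure.

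**A second set of mechanisms** (r = 0.6, a further baseline predictor of outcome, about 1/6 missing overall, slope 1.5) points the same way. With MAR true and dropout in one arm driven by the extra predictor, adjusted completers give 0.346 and imputation 0.299. With MAR false and dropout in one arm driven by the part of the outcome that baseline data do not explain, both give 0.380.

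**Would a delta adjustment work?** At r = 0.5, shifting the imputed intervention scores by the true departure (−0.34) returns 0.301. At r = 0.3 and 0.7, the corresponding shifts return 0.298 and 0.299. In practice the departure is unknown, which is why a range of shifts is needed.

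**The case against.** Section 5.1 asks only whether conclusions are sensitive. It does not claim that the comparison will establish MAR. Re-running under a different missingness assumption is a limited but genuine check, and it can show that dropout is not completely random or that measured predictors matter. That stands, and the analysis is worth keeping. The wording still names MAR as the assumption under test.

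The figures also depend on choices the SAP leaves open.
- **Change scores.** Section 6 also promises a difference in mean change. On that scale, with MAR true, unadjusted completers give 0.249/0.265/0.277, so the distortion has the opposite sign. The gap remains.
- **Imputation model.** Section 6.1 does not say whether group enters it. Without group, imputation gives about 0.25 when MAR holds (0.30 × 5/6) and 0.305/0.296/0.282 when it fails, so the near-agreement with adjusted completers disappears. That is a gap under true MAR, which supports the concern.
- **Mechanism.** If dropout depends on outcome in opposite directions in the two arms, adjusted completers give 0.432 and imputation 0.402. Near-agreement is therefore not universal, although the 0.03 gap understates an error of 0.10.

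Finally, the main case is strongly asymmetric, and the SAP gives no reason to expect that. With 45 completers per arm the adjusted standard error is roughly 0.357 × √(2/45) = 0.075 to 0.477 × √(2/45) = 0.10, so the bias is about 0.5 to 0.7 standard errors. This limits the size of the problem but does not change the logic.

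**Conclusion.** The concern holds. The purpose stated in Section 5.1 is wrong as written: agreement between completers and imputation does not support MAR, and a gap does not refute it. Sections 5.1 to 6.1 contain no analysis that departs towards missing not at random.

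In the illustrated case the unexamined bias is 0.04 to 0.07 logits, or 13% to 23% of the 0.3-logit minimum clinically important difference, and 0.02 to 0.09 over the slopes tried. These sizes rest on an assumed one-sided mechanism, assumed correlations, imputation within arm and an inferred 1/6 missing rate. The true bias could go either way, and it is zero if missing fractions and departures are equal across arms.

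The primary estimate, its stated assumption and the sample size are not affected. The change should be made, because the plan says that its key untestable assumption is checked when it is not.

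**What to change.** - In Section 5.1, call the set complete cases rather than per protocol. Replace the stated purpose with showing whether results depend on the imputation and the covariates used.
- Prespecify one analysis that departs from MAR, built on the imputations already planned in Section 6.1. One option is delta-adjusted imputation of the 3-month AMPS score, with the shift varied separately by arm (including zero and equal shifts) and the tipping point reported.
- State how participants who die before 3 months enter that analysis.

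The cost is some SAP wording and a short loop over planned imputations; no new data are needed. The range of shifts is a judgement that has to be justified. Timing matters: the SAP is dated April 2021 and recruitment was planned to end in December 2020. Section 3 says that "analysis will be performed blinded for group allocation", so the addition must be fixed while that blinding still holds.

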5.2 Subgroups

Due to Covid-19 some participants may not have received the entire intervention at home and therefore subgroup analysis restricted to participants received at least three of the planned visits in own home.

6. Statistical analysis

The primary analysis will be a mixed effect model where group (intervention and control) and municipality are fixed, and the patient is random, assuming dropout is at random. The score at the end of rehabilitation after 3 months will be analysed unadjusted and adjusted for baseline score, age, municipality, gender, fracture and type of operation.

The estimated difference in mean change from baseline to 3 months follow-up and the corresponding 95 % confidence interval (CI) will be presented. Stata (StataCorp. 2019) will be used for the statistical analysis.

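### SAP section 6 does not fix one primary analysis: the listed mixed model does not yield the promised difference in change, and neither the unadjusted nor the adjusted 3-month analysis is ranked as primary

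*SAP*

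**What the plan says.** Section 6 of the SAP makes three statements about the primary analysis.

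- The model: "The primary analysis will be a mixed effect model where group (intervention and control) and municipality are fixed, and the patient is random". No time term and no group-by-time term is listed.
- The score analysed: "The score at the end of rehabilitation after 3 months will be analysed unadjusted and adjusted for baseline score" and for five further covariates, municipality among them. Neither version is called primary.
- The estimate: "The estimated difference in mean change from baseline to 3 months follow-up and the corresponding 95 % confidence interval (CI) will be presented".

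AMPS is measured twice. Section 4.1 puts the first assessment on post-operative days 3 to 5, and then "the AMPS test will be performed, after completed rehabilitation at 3 months follow-up". Section 3 (Randomisation) places the baseline test before allocation and stratifies by municipality. Section 5.1 names ITT as the primary population. Section 6.1 adds that "multiple imputation (MI) will be performed for both primary and secondary outcomes". Neither section 5.1 nor section 6.1 settles the response, the contrast or the covariate set.

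**The concern.** The three statements do not describe the same analysis. A random patient effect implies repeated rows per patient. Analysing the 3-month score implies one row. A difference in change implies a group-by-time contrast, or the change score as response. An analyst following section 6 must add a term or drop the random effect, and must then decide whether baseline and the other covariates enter the primary result.

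These decisions concern the primary test of the primary outcome. If they are left open, they could be made after the results are known. The realised estimate, its confidence interval and, in some trials, its significance depend on them.

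**Working it through.** **Inputs.** From SAP section 3.1: difference 0.30 logits on the AMPS motor scale, SD 0.50, power 0.80, 90 persons in total, so 45 per group at 1:1. Assumed, because the SAP does not give them: two-sided alpha 0.05 (consistent with the 95% interval in section 6), the same SD at both visits, and a correlation r between baseline and 3-month scores of 0.3, 0.5 or 0.7. Triples below are in that order.

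**The plan's own figure.** The SAP states: "The power is set to 0.8 and the standard deviation (SD) is 0.50, which gives a sample size of 90 persons".
- Normal approximation: n per group = 2 × (1.960 + 0.842)² × 0.25 / 0.09 = 43.6, so 44 per group and 88 in total.
- Two-sample t-test: 44.6, so 45 per group and 90 in total.

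The figure reproduces as a plain two-group comparison with SD 0.50. The SAP does not say whether that SD is of the 3-month score or of the change. The sample size is not in dispute.

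**Section 6 fitted literally**

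1. One 3-month row per patient. The patient variance cannot be separated from the residual variance. The group effect can still be estimated, but the random effect is empty.
2. Both visits as rows. The model fits. Without a time or group-by-time term, its group coefficient averages the group difference over the two visits. The expected baseline difference is zero because baseline precedes randomisation, so the expected coefficient is (0 + 0.30)/2 = 0.15. A 200-run simulation at r = 0.5 gave a mean of 0.152; adding group-by-time gave 0.305.
   - SE = √(2/45 × 0.25 × (1 + r)/2) = 0.085 / 0.091 / 0.097.
   - Power, normal approximation = 42 / 38 / 34%. The t version is at most about one point lower.

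**The plausible completions** (noncentral t, all targeting 0.30)

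| Analysis | Variance per patient | SE | Power |
|---|---|---|---|
| Unadjusted 3-month score | 0.25 | 0.105 | 80% at any r |
| Raw change (two-visit model with time and group-by-time, complete data) | 0.5(1 − r) | 0.125 / 0.105 / 0.082 | 66 / 80 / 95% |
| 3-month score adjusted for baseline | 0.25(1 − r²) | 0.101 / 0.091 / 0.075 | 84 / 90 / 98% |

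In each row, SE = √(2/45 × variance).

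**How far the results of one trial can differ**

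- Unadjusted 3-month score against raw change. The two estimates differ by the chance baseline difference, whose SE is 0.105. In 95% of trials they lie within 1.96 × 0.105 = 0.21 logits of each other.
- Unadjusted against all six covariates, simulated at a true 0.30. Assumed: five municipalities of 18, three fracture types, three operation types, and covariates other than baseline not prognostic. The two estimates lie within 0.09 / 0.12 / 0.15 logits in 95% of trials, and the two tests disagree on significance in 9 / 13 / 17%. A separate 6,000-run check gave the same values to rounding.

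**The case against.** The strongest reply is that the intent can be recovered. A random patient effect, dropout assumed at random, two AMPS assessments and a promised difference in change together point to a two-visit repeated-measures model with time and group-by-time left unwritten. On complete data that model returns the raw change difference exactly. The second sentence then describes further analyses of the 3-month score, and baseline enters as a response row rather than as a covariate. This is probably what was meant. But the terms that carry the promised contrast are not in the plan, the plan does not say whether baseline means are constrained to be equal, and nothing subordinates the 3-month analyses to that model.

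Four stronger readings are tempting and are not supported.

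- A reader might infer that the model cannot be run at all. With two rows per patient it runs; the fault is that its group coefficient is the wrong contrast.
- A reader might infer a biased target. The raw change, unadjusted and baseline-adjusted analyses all target the same effect, because baseline precedes randomisation. Only the literal two-visit fit without time terms does not.
- A reader might infer an inflated type I error from having two tests. That would need a rule allowing success on either, and the SAP states none. It is a potential harm only.
- A reader might see a contradiction in municipality being in the primary model and also among the terms "adjusted for baseline score, age, municipality, gender, fracture and type of operation". Municipality is the stratification factor, so unadjusted may simply mean design terms only. This is a minor ambiguity.

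It is also fair that most completions keep the planned power. Among those tabulated, only raw change at r = 0.3 falls clearly below 80%.

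**Conclusion.** The concern holds in this form: a mixed model is labelled primary, but its listed terms do not produce the promised estimate, and the unadjusted and adjusted analyses of the 3-month score are not ranked. No other section of the SAP resolves either gap.

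A literal fit to both visits would halve the estimated effect and roughly halve the power or worse. Among the reasonable completions the loss is in precision and in the room left for choice: power runs from 66 to 98% over the correlations considered, and the unadjusted and six-covariate tests part on significance in about one trial in eleven to one in six.

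The sizes rest on the assumed correlation, alpha and equal SD, and the disagreement rates also on the simulated covariate structure. The conclusion that section 6 fixes no single analysis rests on the text alone. It should be corrected, because it affects the primary test.

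**What to change.** In SAP section 6, name one primary analysis: ANCOVA of the 3-month AMPS score on group, baseline score and municipality, without a random patient effect, fitted in each imputed data set and pooled, in line with section 6.1. State that the group coefficient with its 95% confidence interval is the primary estimate. With baseline as a covariate, this coefficient is the same whether the response is the 3-month score or the change, so the promised difference in change is kept in baseline-adjusted form.

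Equally acceptable is to keep the mixed model, add time and group-by-time with baseline means constrained equal, retain municipality, and name the 3-month group contrast as primary.

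In either case, label as secondary the unadjusted analysis and the one that adds age, gender, fracture and type of operation, and say whether unadjusted still includes municipality.

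The cost is a few lines of SAP text and a small change to the analysis code. No new data are needed, since baseline score and municipality are already collected.
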